8.1 Definitions

Unanticipated Problems Involving Risk to Subjects or Others

Any incident, experience, or outcome that meets all of the following criteria:

- Unexpected in nature, severity, or frequency (i.e. not described in study-related documents such as the IRB-approved protocol or consent form, the investigators brochure, etc)
- Related or possibly related to participation in the research (i.e. possibly related means there is a reasonable possibility that the incident experience, or outcome may have been caused by the procedures involved in the research)
- Suggests that the research places subjects or others at greater risk of harm (including physical, psychological, economic, or social harm).

Adverse Event

An **adverse event** (AE) is any symptom, sign, illness or experience that develops or worsens in severity during the course of the study. Intercurrent illnesses or injuries should be regarded as adverse events.

Abnormal results of diagnostic procedures are considered to be adverse events if the abnormality:

- results in study withdrawal
- is associated with a serious adverse event
- is associated with clinical signs or symptoms
- leads to additional treatment or to further diagnostic tests
- is considered by the investigator to be of clinical significance

Serious Adverse Event

Adverse events are classified as serious or non-serious. A **serious adverse event** is any AE that is:

- fatal
- life-threatening
- requires or prolongs hospital stay
- results in persistent or significant disability or incapacity
- a congenital anomaly or birth defect
- an important medical event

Important medical events are those that may not be immediately life threatening, but are clearly of major clinical significance. They may jeopardize the subject, and may require intervention to prevent one of the other serious outcomes noted above. For example, drug overdose or abuse, a seizure that did not result in in-patient hospitalization, or intensive treatment of bronchospasm in an emergency department would typically be considered serious.

All adverse events that do not meet any of the criteria for serious should be regarded as **non-serious adverse events**.

Preexisting Condition

A preexisting condition is one that is present at the start of the study. A preexisting condition should be recorded as an adverse event if the frequency, intensity, or the character of the condition worsens during the study period.

General Physical Examination Findings

At screening, any clinically significant abnormality should be recorded as a preexisting condition. At the end of the study, any new clinically significant findings/abnormalities that meet the definition of an adverse event must also be recorded and documented as an adverse event.

Post-study Adverse Event

All unresolved adverse events should be followed by the investigator until the events are resolved, the subject is lost to follow-up, or the adverse event is otherwise explained. At the last scheduled visit, the investigator should instruct each subject to report any subsequent event(s) that the subject, or the subject's personal physician, believes might reasonably be related to participation in this study. The investigator should notify the study sponsor of any death or adverse event occurring at any time after a subject has discontinued or terminated study participation that may reasonably be related to this study. The sponsor should also be notified if the investigator should become aware of the development of cancer or of a congenital anomaly in a subsequently conceived offspring of a subject that has participated in this study.

8.2 Recording of Adverse Events

At each contact with the subject, the investigator must seek information on adverse events by specific questioning and, as appropriate, by examination. Information on all adverse events should be recorded immediately in the source document, and also in the appropriate adverse event module of the case report form (CRF). All clearly related signs, symptoms, and abnormal diagnostic procedures results should be recorded in the source document, though should be grouped under one diagnosis.

All adverse events occurring during the study period must be recorded. The clinical course of each event should be followed until resolution, stabilization, or until it has been determined that the study treatment or participation is not the cause. Serious adverse events that are still ongoing at the end of the study period must be followed up to determine the final outcome. Any serious adverse event that occurs after the study period and is considered to be possibly related to study participation should be recorded and reported immediately.

8.3 Reporting of Serious Adverse Events and Unanticipated Problems

8.3.1 Investigator reporting: notifying the IRB

Federal regulations require timely reporting by investigators to their local IRB of unanticipated problems posing risks to subjects or others. The following describes the NYULMC IRB reporting requirements, though Investigators at participating sites are responsible for meeting the specific requirements of their IRB of record.

Report Promptly, but no later than 5 working days:

Researchers are required to submit reports of the following problems promptly but no later than 5 working days from the time the investigator becomes aware of the event:

- ***Unanticipated problems including adverse events that are unexpected and related***
 - *Unexpected: An event is “unexpected” when its specificity and severity are not accurately reflected in the protocol-related documents, such as the IRB-approved research protocol, any applicable investigator brochure, and the current IRB-approved informed consent document and other relevant sources of information, such as product labeling and package inserts.*

- Related to the research procedures: An event is related to the research procedures if in the opinion of the principal investigator or sponsor, the event was more likely than not to be caused by the research procedures.
- Harmful: either caused harm to subjects or others, or placed them at increased risk

Other Reportable events:

The following events also require prompt reporting to the IRB, though no later than 5 working days:

- Complaint of a research subject when the complaint indicates unexpected risks or the complaint cannot be resolved by the research team.
- Protocol deviations or violations (includes intentional and accidental/unintentional deviations from the IRB approved protocol) for any of the following situations:
 - one or more participants were placed at increased risk of harm
 - the event has the potential to occur again
 - the deviation was necessary to protect a subject from immediate harm
- Breach of confidentiality
- Incarceration of a participant when the research was not previously approved under Subpart C and the investigator believes it is in the best interest of the subject to remain on the study.
- New Information indicating a change to the risks or potential benefits of the research, in terms of severity or frequency. (e.g. analysis indicates lower-than-expected response rate or a more severe or frequent side effect; Other research finds arm of study has no therapeutic value; FDA labeling change or withdrawal from market)

Reporting Process

The reportable events noted above will be reported to the IRB using a Reportable New Information submission and will include a description of the event with information regarding its fulfillment of the above criteria, follow-up/resolution, and need for revision to consent form and/or other study documentation. Copies of each report and documentation of IRB notification and receipt will be kept in the Clinical Investigator's study file.

9 Study Oversight

It is the responsibility of the Principal Investigator to oversee the safety of the study at her site. This safety monitoring will include careful assessment and appropriate reporting of adverse events as noted above, as well as the construction and implementation of a site data and safety-monitoring plan. Data safety monitoring will occur on an ongoing basis. There will not be any predefined stopping rules for the entire study, as it does not pose more than minimal risk for study participants.

10 Statistical Considerations

10.1 Study Hypotheses

Hypothesis #1: Family members who participate in Family Connectors (i.e., phone-based parent-to-parent support) will demonstrate improved outcomes at post-test and follow-up as measured by higher self-efficacy, greater perceived social support, and lower caregiver strain in comparison to family members who receive the comparison condition.

Hypothesis #2: Identified clients whose family members who participate in Family Connectors (i.e., phone-based parent-to-parent support) will demonstrate improved outcomes at post-test and follow-up as measured by functioning at school and work in comparison to the comparison condition.

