12.2	INSTITUTIONAL REVIEW BOARD.....	12
12.3	INFORMED CONSENT PROCESS	13
12.3.1	Consent/Assent and Other Informational Documents Provided to Participants	13
12.3.2	Consent Procedures and Documentation.....	13
12.4	PARTICIPANT AND DATA CONFIDENTIALITY	13
13	DATA HANDLING AND RECORD KEEPING.....	14
13.1	DATA COLLECTION AND MANAGEMENT RESPONSIBILITIES	14
13.2	STUDY RECORDS RETENTION	15
13.3	PROTOCOL DEVIATIONS	15
13.4	PUBLICATION AND DATA SHARING POLICY	15
14	STUDY FINANCES	15
14.1	FUNDING SOURCE.....	15
14.2	COSTS TO THE PARTICIPANT.....	15
14.3	PARTICIPANT REIMBURSEMENTS OR PAYMENTS	15
15	STUDY ADMINISTRATION	16
15.1	STUDY LEADERSHIP	16
16	CONFLICT OF INTEREST POLICY	16
17	ATTACHMENTS	17

[figure not shown]
List of Abbreviations

AE	Adverse Event/Adverse Experience
CFR	Code of Federal Regulations
CRF	Case Report Form
DCC	Data Coordinating Center
FFR	Federal Financial Report
HIPAA	Health Insurance Portability and Accountability Act
IRB	Institutional Review Board
MOP	Manual of Procedures
N	Number (typically refers to participants)
NIH	National Institutes of Health
NYC H+H	New York City Health + Hospitals
OHRP	Office for Human Research Protections
PI	Principal Investigator
QI	Quality Improvement
SAE	Serious Adverse Event/Serious Adverse Experience
US	United States

Protocol Summary

Title	Examining the Impact of Family Connectors
Short Title	Family Connectors
Brief Summary	This study will examine the impact of Family Connectors amongst 96 family members of adolescents/young adults with first episode psychosis who were discharged from OnTrack.
Objectives	The study objectives are to examine the association between involvement in Family Connectors, a manualized peer-to-peer support and education program for family members of adolescents or young adults with symptoms of first episode psychosis, and feelings of empowerment, self-efficacy and social support. A total of 96 family members will be enrolled in this study, and will be enrolled in either Family Connectors + a packet of community resources or the community resource alone. Outcomes consist of the family member's feelings of self-efficacy, connection to services and supports, caregiving strain, satisfaction, and perceptions of adolescent/young adult functional outcomes at school and work.
Methodology	RCT with data collection and baseline (T1), follow-up (one-month post-baseline, T2) and posttest (six months past T2xx).

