This study will observe the impact of the Family Connectors (FC) model on family members who participated in OnTrack, a treatment program for adolescents/young adults with symptoms of first episode psychosis. The Family Connectors Program is a manualized program that uses a time-limited parent-to parent (i.e. peer parent) support and education program delivered by phone to families of youth with serious mental health difficulties, assisting family members in becoming fully engaged with provider teams who coordinate and provide care. Family Connectors is delivered weekly by phone over the course of between three and six months.

This study has potential for significant impact in five ways: (1) it addresses a high-cost, serious, and significantly debilitating condition (FEP) with the goal of improving client outcomes; (2) it builds on a major national policy initiative and a state-wide priority in NYS; (3) it embeds an intervention tested in prior trials into Coordinated Specialty Care (CSC), enhanced with specialized engagement training offered by Co Lead [name], a prominent mid-career researcher with expertise in engagement of low-income families of color; (4) the model is scalable, as it uses a low-cost, low-intensity enhancement strategy, improving potential for broad scaling in other states; and (5) it is nested within publicly-funded mental health (MH) sites that disproportionately serve low-income Y/YA.

Family Connectors provides emotional support (i.e., reducing parental stress and social isolation through providing emotional support), informational support (i.e., reducing parental stress and social isolation through providing emotional support), informational support (e.g., enhancing parental access to resources and information), positive attitudes (i.e., helping parents develop positive attitudes toward the importance of social support, perceived control, and expected benefits and actions), and caregiver strain.

We are seeking IRB approval to study the impact of Family Connectors upon family member outcomes (e.g., self-efficacy, caregiver strain, satisfaction with the program, social supports), and perceptions of their relative's (adolescents/young adults who participated in OnTrack) function and school outcomes.

2.2 *Rationale*

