The study seeks to understand the impact of Family Connectors amongst a sample of family members who participated in OnTrack with their adolescent/young adult family member. Specifically, we seek to examine the impact of FC upon family member outcomes (e.g., self-efficacy, satisfaction with the program, engagement in supports), and functional outcomes and service use amongst adolescents/young adults.

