3.1 Primary Objective

The purpose of this study is to examine the association between involvement in Family Connectors, a manualized peer-to-peer support and education program for family members who participated in OnTrack, a treatment program for adolescents/young adults with first episode psychosis. A total of 96 family members will be enrolled in this study; of them, 48 will be randomly assigned to Family Connectors + a packet of community resources, and 48 will receive the community resource packet alone. Outcomes will consist of caregiver self-efficacy, strain, connection to services, satisfaction with the program, and functioning of the adolescent/young adult at school and work.

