7.1 Questionnaire Administration

Study measures include one questionnaire that taps into the following domains: (1) sociodemographic characteristics of the family member, (2) family member perceived self-efficacy, (3) family member/caregiver social support, caregiver strain, satisfaction with Family Connectors, and (4) the adolescent/young adult's functioning at school and work. The questionnaire will be collected via REDCap at three time points (with the exception of the sociodemographic questionnaire, which will be collected at T1 only, and satisfaction questions, which will be collected at T3 and T4 only).

See the Appendix for a copy of the measures.

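### Hypothesis 2 and sections 2.2 and 3.1 state the client's own functioning as the outcome, but the only planned source is an unmasked family member's report

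*Combined protocol and SAP*

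**What the plan says.** The protocol words this outcome in two ways.

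**As the client's own functioning**
- Section 10.1, Hypothesis 2: the client is the subject of the sentence, and clients in the Family Connectors arm "will demonstrate improved outcomes at post-test and follow-up as measured by functioning at school and work in comparison to the comparison condition".
- Section 3.1, in the list of outcomes: "functioning of the adolescent/young adult at school and work".
- Section 2.2, in the statement of aims: "functional outcomes and service use amongst adolescents/young adults".

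**As the family member's view**
- Protocol Summary, Objectives: "perceptions of adolescent/young adult functional outcomes at school and work".
- Section 2.1, in the request for IRB approval: "perceptions of their relative's (adolescents/young adults who participated in OnTrack) function and school outcomes".

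On the data source, section 7.1 reads "Study measures include one questionnaire that taps into the following domains". The fourth domain is "the adolescent/young adult's functioning at school and work", and it sits beside the family member's own self-efficacy, social support, strain and satisfaction. Section 5.1 enrols adult family members, plus Family Connectors for qualitative interviews. Section 10.3 plans only bivariate and multivariate comparisons.

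**The concern.** The hypothesis is about one person and the data come from another. That other person receives the intervention and cannot be kept unaware of the arm. If family members in the Family Connectors arm come to see or describe their relative more favourably, the arms will differ on this outcome even if no client has changed. Someone testing Hypothesis 2 as worded would then conclude that clients improved at school and work, which these data cannot establish on their own. Hypothesis 1 does not have this mismatch, because there the family member is both the subject and the source.

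**Working it through.** **Step 1: is there any source other than the family member?** None is named. Section 5.1 enrols no clients, section 7.1 lists one questionnaire, and the Schedule of Events lists only consent and assessment. No client self-report, school or employment record, clinician rating or independent assessor is planned for this outcome. Sections 11 and 12.4 mention medical records in general terms but do not tie them to functioning.

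**Step 2: can the reporter be masked?** Blinding is not mentioned anywhere, so this is an inference from the design. Section 6.2 gives weekly calls for three to six months, section 4.1 makes the comparator a waitlist, and section 5.4 tells recruits that everyone can eventually have a Family Connector. A respondent cannot fail to know which arm they are in.

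**Step 3: does the intervention act on the reporter?** Yes. Section 2.1 lists lower parental stress and isolation, caregiver strain, and "helping parents develop positive attitudes toward the importance of social support"; the same list goes on to perceived control and expected benefits. Hypothesis 1 predicts higher self-efficacy and lower strain in the same person who describes the client.

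**Step 4: can the analysis separate the two explanations?** No. Section 10.3 names no method for it, and with one informant there is no second measurement to compare against.

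**Step 5: illustration of size.** The plan has no figure to reproduce. The 96 in section 10.2 is an expected participation count (96/150 = 64% of a year's families), with no alpha, power, effect size or SD.

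Inputs: 48 per arm (section 3.1). Assumed: two-sided 5% test, continuous outcome with SD 1, no attrition, true client effect of zero, reporting shift of b SD.

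- Standard error of the standardised difference: √(2/48) = 0.204.
- Noncentrality: b/0.204, with 96 − 2 = 94 degrees of freedom.

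| Assumed shift b | b/0.204 | P(significant), noncentral t | P(significant), normal approximation |
|---|---|---|---|
| 0 | 0 | 5.0% | 5.0% |
| 0.1 SD | 0.49 | 7.7% | 7.8% |
| 0.2 SD | 0.98 | 16.3% | 16.5% |
| 0.3 SD | 1.47 | 30.7% | 31.2% |

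Counting only results that favour Family Connectors, the noncentral t values are 7.0%, 16.1% and 30.7% against a nominal 2.5%. With an assumed 20% loss (48 × 0.8 ≈ 38 per arm), the normal approximation gives 14.1% at 0.2 SD and 25.8% at 0.3 SD.

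**The case against.** The other side has five arguments.

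- **The proxy source is disclosed.** The Summary and section 2.1 both say perceptions, and family report is a legitimate measure. This stands. The choice of informant is not the defect; the defect is that the hypothesis, the objective and the rationale claim more than that informant can show.
- **The attitudes in section 2.1 are not about the client's functioning.** They concern social support, perceived control and expected benefits. This also stands. A reader might infer that the programme sets out to change how caregivers rate their relative, and the documents do not say so. A spillover into those ratings is plausible, not shown.
- **The questionnaire was not available to this review.** If the functioning domain asks about status, such as being enrolled or employed, a shift is less likely than with rating scales. This bears on the size of the risk and on the fix, but not on the mismatch in wording.
- **The percentages are ordinary power figures at 48 per arm.** This is correct. They show what a given shift would do, and are no evidence that one will occur.
- **Nothing says a positive result will be published as client improvement.** No reporting statement says so, but that is the conclusion Hypothesis 2 states.

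**Conclusion.** The point holds as a mismatch between claim and measurement. Three sections assert client functioning, two describe family perception, and the planned data support only family report from someone who knows the arm. A positive Hypothesis 2 result would be compatible with a reporting shift, a real client change, or both.

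The size cannot be derived from the documents. The 8%, 16% and 31% rest on assumed shifts and on a test, a scale type and complete follow-up that the plan does not state.

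Two stronger readings are not supported. A reader might infer that any difference must be a change in perception only; that overcorrects, since family report can also pick up real change. A reader might also infer that the outcome should become secondary. Section 3.1 lists it under the primary objective, section 3.2 gives no secondary objectives, and a problem with the source of the data does not in itself settle an outcome's rank.

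**What to change.** 1. In sections 2.2, 3.1 and 10.1, describe this outcome as *family-member-reported functioning of the client at school and work*, in line with the Protocol Summary and section 2.1.
2. In section 10.3, state that a positive Hypothesis 2 result will be reported as a difference in family-member-reported functioning from an unmasked reporter and not, on its own, as demonstrated client improvement.
3. If the questionnaire has factual status items (enrolled, employed), prespecify that they are analysed and reported ahead of rating items, because they are less open to a reporting shift.
4. Leave the outcome's rank as it is; this point gives no ground to relabel it as secondary.

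The cost is wording in four sections and, if item 3 applies, a stated order of analysis. No new data, participants or visits are needed. The downside is a more modest claim.

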10.2 Sample Size Determination

Our sample size was calculated based upon OnTrackNY's annual enrollment numbers; specifically, there are approximately 150 families who graduate each year from Family Connectors; based upon this number, we anticipate 96 will participate.

10.3 Statistical Methods

Univariate statistics will be employed to describe the sample characteristics. Categorical data will be presented in percentages; interval and ratio-level data will be presented via measures of central tendency and dispersion (e.g., means, standard deviations). Bivariate and multivariate analyses will be conducted in order to examine between and within group differences in outcomes.

11 Source Documents and Access to Source Data/Documents

Source data is all information, original records of clinical findings, observations, or other activities in a study necessary for the reconstruction and evaluation of the study. Source data are contained in source documents. Examples of these original documents, and data records include: hospital records, clinical and office charts, laboratory notes, memoranda, subjects' diaries or evaluation checklists, pharmacy dispensing records, recorded data from automated instruments, copies or transcriptions certified after verification as being accurate and complete, microfiches, photographic negatives, microfilm or magnetic media, x-rays, subject files, and records kept at the pharmacy, at the laboratories, and at medico-technical departments involved in the study.

The study case report form (CRF) is the primary data collection instrument for the study. All data requested on the CRF must be recorded. All missing data must be explained. If a space on the CRF is left blank because the procedure was not done or the question was not asked, write "N/D". If the item is not applicable to the individual case, write "N/A". All entries should be printed legibly in black ink. If any entry error has been made, to correct such an error, draw a single straight line through the incorrect entry and enter the correct data above it. All such changes must be initialed and dated. DO NOT ERASE OR WHITE OUT ERRORS. For clarification of illegible or uncertain entries, print the clarification above the item, then initial and date it.

Access to study records will be limited to IRB-approved members of the study team. The investigator will permit study-related monitoring, audits, and inspections by the IRB/EC, the sponsor, government regulatory bodies, and University compliance and quality assurance groups of all study related documents (e.g. source documents, regulatory documents, data collection instruments, study data etc.). The investigator will ensure the capability for inspections of applicable study-related facilities.

Participation as an investigator in this study implies acceptance of potential inspection by government regulatory authorities and applicable University compliance and quality assurance offices.

12 Ethics/Protection of Human Subjects

